1.0 Background

- 1.1 Worldwide, nearly 1.3 million patients are diagnosed with and more than 600 000 patients die from colorectal cancer every year (Ferlay et al, 2013). Regorafenib is a novel oral multikinase inhibitor that blocks the activity of several protein kinases, including kinases involved in angiogenesis, oncogenesis and tumor microenvironment (Kies et al, 2010). Regorafenib was recently shown to provide a survival benefit in metastatic colorectal cancer patients who have progressed after all standard therapies (Grothey, et al). This led to its approval in September 2012 by the FDA for use in the United States. Despite the observed benefits in a patient population with no current standard, toxicities such as Palmar-plantar erythrodysesthesia syndrome (PPES) (which occurs early in the first 1-2 weeks) and fatigue have widely limited its use in the US. Multiple practices across the US have adopted, and despite the absence of supportive data, various dosing or interval scheduling including starting at lower doses and escalate as tolerated, every other week dosing intervals and other.

In this study, we propose to design a novel strategy to optimize the dose of regorafenib in patients with refractory mCRC to allow maintenance of the observed benefits while improving the tolerability profile. The proposed strategy, arm A (combining A1 and A2) consists of starting regorafenib at 80 mg/day for 1 week (week1), then if no significant drug-related toxicities escalate to 120 mg/ day for another week (week 2), then again if no significant related toxicities escalate to a total dose of 160 mg/day (week 3) followed by a week break (week 4 of cycle 1). If at the end of week 1, week 2 or week 3 toxicities are unacceptable as defined by the study, the decision will be to deescalate by 40 mg/day and there will be no further dose escalations. A comparative arm, arm B (combining B1 and B2) will include a standard dose/schedule regorafenib of a 160 mg/day starting on day 1 of cycle 1. The primary goal of this study is to compare the proportions of patients on each arm who complete 2 cycles of protocol treatment and initiate cycle 3. We will also assess other outcome and quality of life measures and toxicity profile with a focus on regorafenib related toxicities. We will also assess a potential strategy to reduce the severity of PPES. Additionally, we will perform limited PK analysis in both arms.

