2.3 Correlative Research

- 2.31 Evaluate and compare trough (C_{\min}) PK during the first 2 treatment cycles for regorafenib and active metabolites M2, M5 between the low dose (dose escalation) and the standard dose cohorts, and correlate with toxicity profile.
- 2.32 Evaluate the correlation between PK parameters and tumor response/stable disease after the first two cycles.
- 2.33 Evaluate the correlation between PK parameters and PFS and OS.
- 2.34 Evaluate if trough (C_{\min}) concentrations are associated with patient-specific factors (such as – but not limited to – age and concomitant medications).

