4.0 Test Schedule

Tests and procedures	Active Monitoring Phase										
	≤7 days prior to randomization	Cycle 1 ¹³				Cycle 2 ¹³				After week 8: Every 4 weeks until progression (+/- 3 days)	At PD, withdrawal or removal
		Week 1 (Day 1)	Week 2 (Day 8)	Week 3 (Day 15)	Week 4 (Day 22)	Week 1 (Day 1)	Week 2 (Day 8)	Week 3 (Day 15)	Week 4 (Day 22)		
History and exam, weight, ECOG PS ¹² , blood pressure	X	X ¹²	X	X	X	X	X	X	X	X	X
Height	X										
Adverse event assessment ⁸	X		X	X	X	X	X	X	X	X	X
Hematology ^{8, 11} : CBC/ differential, ANC, INR/PTT ^{8, 10}	X	X				X				X	
Chemistry ^{8, 11} : SGOT (AST), alk phos, T. bili, serum creatinine, calcium, glucose, Na, K, SGPT (ALT)	X	X		X ⁷		X ⁷		X ⁷		X	
Albumin	X										
Urine proteinuria or urine protein creatinine ratio	X										
Tumor measurement ⁸ (CT scan of chest, abdomen and pelvis) (MRI if CT is not feasible)	X ¹								X ¹	X ¹	X ^{1,9}
ECG ⁶	X										
Serum pregnancy test	X ²										
Mandatory blood sample (see Section 14.0)	X ^{4,R}	(Day 7) X ^{4,R}	(Day 14) X ^{4,R}	(Day 21) X ^{4,R}		(Day 1) X ^{4,R}		(Day 21) X ^{4,R}			
Patient Medication Diary (Appendix II) ³		X	X	X	X	X	X	X	X	X	
Patient Questionnaire Booklets (Appendices IV, V, VI)	X ⁵		X ^{5,8}			X ^{5,8}	X ^{5,8}		X ^{5,8}		

1. CT scans preferred (MRI if CT is not feasible) of the chest, abdomen and pelvis. Use same imaging throughout the study. Tumor measurements at baseline (≤28 days prior to randomization) and every 8 weeks until progression.
2. For women of childbearing potential only.

3. The diary must begin the day the patient starts taking the medication and must be completed per protocol and returned to the treating institution weekly during Cycles 1 and 2 and every 4 weeks thereafter.
 4. Kits are required for this collection. Samples will be collected for PK analysis of C_{min} of regorafenib, M2 and M5 at the following time points: Cycle 1, days 7, 14 and 21 prior to treatment; Cycle 2, days 1 and 21, prior to treatment. Samples will be collected for research banking at the following time points: Baseline, prior to treatment; Cycle 2, days 1 and 21, prior to treatment. See Section 14.0 for specific instructions.

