- 16.46 Furthermore, patients will be descriptively compared between treatment arms and between HFS treatment strategies (pre-emptive vs. reactive) according to self-reported outcomes given on the HFS14 questionnaire. See Section 2.24. Results from the cycle 1 and 2 HSF14 questionnaires will also be summarized descriptively as they relate to the pre-emptive versus reactive PPES strategies, with comparisons made within and between arms using the t-test or Wilcoxon rank sum test as appropriate, as well as taking time-dependence into account. Changes in QOL (according to the LASA questionnaire as measured by the overall QOL question) from baseline will also be compared between the treatment arms using the t-test or Wilcoxon rank sum test. We hypothesize that patients receiving regorafenib will experience greater deficits in QOL as reflected by scores on the HSF14, the BFI and the LASA. These questionnaires have specific application to this population. See Section 2.24.
- 16.47 Pharmacokinetic Analysis
- The samples will be analyzed for the regorafenib concentrations using liquid chromatography mass spectrometry, with the anticipated method being a modified version

of that published by Van Erp et al. The samples will be analyzed for M2 and M5, if cost-free standards can be obtained from Bayer.

After quantitation, the average regorafenib concentration will be calculated by arms (Arm A vs. B) at each time point.

As exploratory analysis, this average concentration will be correlated with toxicity and efficacy endpoints. Further descriptive characteristics of the pharmacokinetics will also be calculated. An example includes (but is not limited to) within-patient variability in the trough concentrations pharmacokinetic parameters will also be calculated, both overall and within cycles, as a ratio of the maximum:minimum value.

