16.8 Missing Data

Patients with missing data will be excluded from relevant analyses; no imputation of missing data will be performed.

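### The PK correlation in 16.47 defines no patient-level exposure, and any version using troughs after Cycle 1 Day 7 is partly a consequence of toxicity

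*Combined protocol and SAP*

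**What the plan says.** Section 2.3 sets the goals. Trough concentrations in the first two cycles are to be compared "between the low dose (dose escalation) and the standard dose cohorts, and correlate with toxicity profile". They are also to be related to response or stable disease after two cycles, and a further goal reads "Evaluate the correlation between PK parameters and PFS and OS".

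Section 16.47 is the matching analysis text. It states that "the average regorafenib concentration will be calculated by arms (Arm A vs. B) at each time point", and then "As exploratory analysis, this average concentration will be correlated with toxicity and efficacy endpoints". It names no correlation method, no adjustment for arm or dose, no time ordering, and no landmark or time-varying exposure.

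The Section 4.0 footnote gives the PK samples: "Cycle 1, days 7, 14 and 21 prior to treatment; Cycle 2, days 1 and 21, prior to treatment". Section 1.1 makes Arm A's first dose step conditional: "then if no significant drug-related toxicities escalate to 120 mg/ day for another week (week 2"). The step to 160 mg has the same condition, and unacceptable toxicity leads to a lower dose with no further escalation. The tables in 8.1 to 8.3 add reductions, interruptions and discontinuation for toxicity across both arms. Patients who stop treatment go to event monitoring (Section 13), where the form schedule in 18.1 lists no PK specimen. Section 16.8 adds: "Patients with missing data will be excluded from relevant analyses; no imputation of missing data will be performed". PFS and OS run from randomization (16.41, 16.42).

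**The concern.** There are two linked problems.

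First, the unit of analysis is undefined. Two arms and five sampling times give at most 2 x 5 = 10 arm-level means. These cannot be correlated with whether a given patient had toxicity or how long that patient lived. The analyst will have to choose a patient-level exposure, and the plan does not say which.

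Second, the choice matters. A trough drawn after Day 7 reflects a dose that toxicity may already have lowered, or that absence of toxicity allowed to rise. Tolerant patients then show high troughs because they were escalated or kept at full dose. A correlation with toxicity that ignores time order can suggest that higher exposure goes with less toxicity when there is no relation, or can weaken a real positive one.

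Section 1.32 gives the link between concentration and toxicity or efficacy as a main reason for the PK work, in a trial meant to optimize dose. A wrong sign could be read as evidence about exposure.

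**Working it through.** **The plan's own figure.** The PK correlation has none. The only stated size is 110 patients, 55 per pooled arm (16.3). It reproduces: exact Fisher power for 45% against 63% at one-sided alpha 0.20 is 0.804 with 55 per arm. So n=55 is used for Arm A.

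**Inputs from the documents.** Arm A doses of 80, 120 and 160 mg in weeks 1 to 3; a fall from 120 to 80 mg after significant toxicity (8.1); AUC CV 77.8-182.4% (1.31), taken as 78-182% for troughs; exposure less than dose-proportional above 60 mg (1.31).

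**Assumptions, not in the documents.** Toxicity risk p of 15% or 25% per week, unrelated to concentration; patients with week-1 toxicity give no later sample; trough proportional to dose^b, with b = 1 or 0.5.

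**Expected bias at Day 21, Arm A.** Patients with toxicity who still give a Day 21 sample had it in week 2 (now on 80 mg) or week 3 (still on 160 mg when sampled).
- Share on 80 mg = p / [p + (1-p)p] = 1/(2-p): 0.54 at p=15%, 0.57 at p=25%.
- Geometric mean ratio, toxicity to no toxicity, = 0.5^(b x share). For b=1: 0.69 and 0.67. For b=0.5: 0.83 and 0.82. With no true effect it should be 1.

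**False-positive rate, worked at p=15%.**
- Sampled at Day 21: 55 x 0.85 = 46.75. With toxicity: 46.75 x (1 - 0.85^2) = 13.0. Without: about 34.
- Log-scale SD = sqrt(ln(1+CV^2)): 0.689 at CV 78%, 1.209 at CV 182%.
- SE = SD x sqrt(1/13 + 1/34) = SD x 0.326: 0.225 and 0.394.
- b=1: difference 0.54 x ln 2 = 0.375, or 1.67 and 0.95 SE. Against a critical value of 1.96 this rejects about 39% and 16% of the time.
- b=0.5: difference 0.187, or 0.83 and 0.47 SE; about 13% and 8%.

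This approximation ignores the spread of doses within the toxicity group. Simulation of the same model over both values of p and both CVs gave:

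| Exposure, Arm A | Trough proportional to dose | Square root of dose |
|---|---|---|
| Day 21 trough | about 15-41% | about 7-15% |
| Day 7 trough | about 5% | about 5% |

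For a patient mean over cycle 1, across both scalings, the rate was about 5-10% if only patients with all three samples are used and about 6-26% if available samples are averaged. The plan does not say which would apply.

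**Both arms, different model.** This used 110 patients, Spearman correlation, assumed weekly toxicity 8-15%, 25% stopping after toxicity and no true effect. Mean rho with toxicity was about 0.00 at Day 7 (4.5-6% of runs with p<0.05), -0.18 to -0.21 at Cycle 2 Day 21 (26-29%), and -0.07 to -0.08 for a five-sample patient mean (11-12%). With a true positive effect, rho was 0.23 at Day 7, 0.19 for the five-sample mean and 0.07 at Cycle 2 Day 21.

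**PFS, same model.** Rho was about 0 at single time points. Only patient means over available samples moved: +0.07 to +0.11 in Arm A (Cycle 2 Day 1 left out) and -0.09 to -0.11 in Arm B (Cycle 2 Day 1 included).

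**Cycle 2 Day 1.** This sample follows the off-week. At a half-life of 20-30 h, 0.5^(168/20) = 0.3% to 0.5^(168/30) = 2% of the parent-drug level remains after 168 h. It is not an on-treatment trough.

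**The case against.** **A reader might infer that the plan averages each patient's concentrations over cycles 1 and 2.** It does not. The average in 16.47 is by arm at each time point, and no per-patient average is defined. The averaged measures are also the less affected ones.

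**A reader might infer immortal-time bias for PFS and OS generally.** The documents do not support that at a single time point. Every patient with that sample was alive when it was drawn, so a landmark only moves the origin by a near-constant. The last PK sample falls at about study day 28 + 21 = 49, before the first scheduled scan in Cycle 2 Week 4. When shared frailty was allowed to drive both toxicity and PFS, the effect at Cycle 2 Day 21 was small (rho 0.00-0.06, 6-7% false positives). For multi-sample averages the sign differed between arms, so no single direction can be claimed.

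**The sizes are assumed.** Weekly toxicity is not in the documents, and AUC variability stands in for trough variability. The larger range needs dose-proportional troughs, while 1.31 says less than proportional. What happens after toxicity at 80 mg is also open to reading: Section 1.1 speaks of lowering by 40 mg, the cell in 8.1 holds a dash, and 8.12 takes doses below 80 mg off treatment. Those passages need to be reconciled.

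**Day 7 has limits.** Section 1.1 places PPES in the first 1-2 weeks, so early events may be lost. In Arm A, Day 7 reflects only the starting dose. M5, with a half-life of 40-100 h (1.31), has reached only 69-95% of steady state after 168 h. The PPES table allows dose changes at first occurrence, so a few Day 7 samples may already follow one.

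All of this narrows the point. It does not remove the dependence of later dose on toxicity, or the absence of any stated handling of it.

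**Conclusion.** The point holds for toxicity. Section 16.47 has no usable unit of analysis, and any patient-level exposure built on samples after Day 7 is partly caused by the outcome it is meant to explain. In Arm A, under the assumptions stated, a nominal 5% test on the Day 21 trough is wrong about 15-41% of the time with dose-proportional troughs and about 7-15% with square-root scaling. Cycle 1 means fall between about 5% and 26%, depending on how missing samples are handled. These are illustrations of scale, not predictions for this trial; the direction and the Day 7 contrast are firmer than the percentages.

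For PFS and OS the point is conditional: it applies if several samples are averaged per patient, and hardly at all at one time point. The analysis is labelled exploratory, has no stated alpha or decision attached, and leaves the primary comparison untouched. It is still worth changing, because the correlations are stated goals and a better method needs no new data.

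**What to change.** Revise 16.47 as follows.

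1. Define a patient-level exposure and require that it precede the outcome. State how patients with missing samples are handled for that measure.
2. Toxicity: relate the Cycle 1 Day 7 trough, stratified by arm, to first Grade 3-4 PPES or fatigue after that sample. Also fit the most recent trough before onset as a time-varying exposure, stratified by arm, up to the first event.
3. Report later troughs and whole-period averages against toxicity descriptively only. Keep Cycle 2 Day 1 separate from on-treatment troughs.
4. PFS and OS: if a multi-sample average is used, count time from the last sample used, among patients event-free then, or treat exposure as time-varying. For a single time point this changes little.

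The cost is wording in the analysis section; no new samples or visits are needed. The downside should be stated in the plan: events before Day 7 drop out of these analyses, which may be a material share given the early onset of PPES, and Day 7 in Arm A says nothing about exposure at the higher doses. Reporting the number of events before Day 7 by arm would let readers judge that loss.

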1.3 Correlative Research

1.31 Regorafenib clinical pharmacokinetics

Regorafenib and its metabolites M2 and M5 have been assessed pharmacokinetically in several phase I studies, both with regorafenib dosed 21 days on/7 days off (Mross K et al. 2012; Strumberg D et al. 2012; Sunakawa Y et al. 2014), and with continuous dosing (Kies MS et al. 2010; Finn RS et al. 2013). Based on safety, efficacy and PK analysis (higher exposure on dosing days), the final dose taken into phase III studies was 160 mg 21 days on/7 days off.

Regorafenib is moderately fast absorbed after oral administration with median t_{max} of 3 to 4 hours, and mean C_{max} of 2.5 mg/L. Steady-state is expected to occur within 7 days after first administration. The overall mean terminal half-life at steady state is 20-30 hours, with a $t_{max,ss}$ of 5 hrs. Mean $C_{max,ss}$ and $AUC_{(0-24)ss}$ with 160 mg dosing were 3.9 mg/L and 58.3 mg•h/L. In the dose escalation phase I studies, regorafenib PK at doses above 60 mg was less than dose proportional. Accumulation of regorafenib from day 1 to day 21 was consistent with linear pharmacokinetics (Mross K, et al .2012).

Regorafenib has 2 major active metabolites, M2 and M5. While both regorafenib and M2 have elimination half-lives of 20-30 hrs, the M5 active metabolite has a half-life of 60 hrs (range 40-100 hrs).

Regorafenib and its active metabolites have substantial variability in their plasma exposure – expressed as either the maximum concentration shortly after administration (C_{max}) or the area under the concentration-time curve (AUC) – after oral regorafenib administration. The coefficient in variation (standard

deviation/mean) of C_{\max} ranges from 61.9% to 173.5%, showing considerable interpatient variability in the absorption. This is not unexpected since regorafenib's absorption is influenced by the fat content in the diet (Section 15.15). Similarly, the AUC has substantial variability with the CVs ranging from 77.8 to 182.4%. This is also not unexpected since regorafenib undergoes enterohepatic recirculation, and is susceptible to a multitude of drug interactions since it is a CYP3A4 and UGT1A9 substrate (Section 15.15). Furthermore, within-patient variability is present such that an individual patient can have dose-to-dose variability in their pharmacokinetics.

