1.32 Rationale for regorafenib pharmacokinetic studies

Regorafenib has clinical activity in CRC, but many patients discontinue treatment in the first 2 cycles due to adverse events (Grothey A et al. 2013). In the few phase I studies to date, small patient numbers underwent any PK evaluation at steady state beyond cycle 1, to understand a possible connection between toxicity and PK parameters.

Because this clinical trial seeks to optimize the regorafenib dose and overall exposure in patients with refractory mCRC, it is critical that we evaluate the pharmacokinetic parameters of regorafenib and its metabolites, and assess whether their PK variability is clinically relevant. To our knowledge, no large pharmacokinetic correlative studies – or those studies evaluating if plasma regorafenib concentrations are associated with its efficacy or toxicity – have been conducted to date.

Therefore, as detailed in Section 14.1, we have developed a clinic-friendly sampling schedule to collect the PK trough levels (C_{\min}) for the study drug and its metabolites, to maximize patient compliance. In the low dose (dose escalation) cohort, as the regorafenib dose is planned to be escalated weekly in cycle 1 from 80 to 120 to 160mg, trough levels will be collected on days 7, 14 and 21, when each regorafenib dose would be expected to reach steady state. These visits coincide with regular clinic visits for safety/toxicity evaluation. In cycle 2, PK will be collected on days 1 and 21. To be able to compare the low dose, escalating cohort with the standard dose cohort, similar time-points for PK analysis were chosen.

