- 6.22 After the patient has been registered into the study, the patient will be assigned to one of the following treatment groups, in 1:1:1:1 fashion, using the Pocock and Simon dynamic allocation procedure which balances the marginal distributions of the stratification factors between the treatment groups (Pocock-Simon, 1975).
- Arm A 1: Regorafenib Cycle 1: 80 mg daily Week 1/120 mg daily Week 2/160 mg daily week 3 then 1 week off followed by Cycle 2+ (160 mg for 21 days/1 week off) + pre-emptive strategy for PPES starting Cycle 1 Day 1
 - Arm A 2: Regorafenib Cycle 1: 80 mg daily week 1/120 mg daily week 2/160 mg daily week 3 then 1 week off followed by Cycle 2+ (160 mg for 21 days/then 1 week off) + reactive strategy for PPES
 - Arm B 1: Regorafenib 160 mg daily for 21 days/then 1 week off + pre-emptive strategy for PPES starting Cycle 1 Day 1
 - Arm B 2: Regorafenib 160 mg daily for 21 days/then 1 week off + reactive strategy for PPES

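### In section 16.47 the cycle 1 max:min trough ratio is confounded with Arm A's planned dose escalation, so it is neither a clean measure of within-patient variability nor comparable between arms

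*Combined protocol and SAP*

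**What the plan says.** Section 16.47 lists, under further descriptive characteristics of the pharmacokinetics, that "within-patient variability in the trough concentrations pharmacokinetic parameters will also be calculated, both overall and within cycles, as a ratio of the maximum:minimum value". It states no dose adjustment, no log-scale SD or CV, and no minimum number of samples.

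The sampling and dosing that feed this ratio are set elsewhere:

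- **Arm A, cycle 1 (section 1.32):** "the regorafenib dose is planned to be escalated weekly in cycle 1 from 80 to 120 to 160mg", and "trough levels will be collected on days 7, 14 and 21, when each regorafenib dose would be expected to reach steady state". Each of the three troughs therefore belongs to a different planned dose.
- **Arm B (section 6.22):** "Regorafenib 160 mg daily for 21 days/then 1 week off", so the planned dose is constant over the same three troughs.
- **Cycle 2 (section 1.32):** "In cycle 2, PK will be collected on days 1 and 21". Day 1 is a pre-dose sample after the week off.
- **Dose and exposure (section 1.31):** "regorafenib PK at doses above 60 mg was less than dose proportional". No exponent is given.
- **True variability (section 1.31):** "within-patient variability is present such that an individual patient can have dose-to-dose variability in their pharmacokinetics". No within-patient CV is given.
- **Missing data (section 16.8):** patients with missing data are dropped from the analyses concerned, without imputation. The section does not say whether one missing trough removes a patient from the ratio.

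**The concern.** A maximum divided by a minimum reflects within-patient variability only if the quantity would otherwise be constant. In Arm A it is designed to change from week to week; in Arm B it is not. The same statistic then means different things in the two arms.

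Section 1.32 wants to know whether PK variability is clinically relevant, and goals 2.31 to 2.33 relate PK to toxicity, response, PFS and OS. A patient-level variability measure that already contains the dosing history is a poor starting point. In Arm A, a patient who tolerates escalation gets a larger ratio than one who is stepped down. In Arm B, a patient who is dose-reduced gets a larger ratio than one who is not. The measure therefore carries tolerability, in opposite directions in the two arms.

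**Working it through.** The documents give no value for this ratio, so there is no stated figure to reproduce. The check asks what the rule returns under the planned schedule.

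**Inputs from the documents.** Planned doses 80/120/160 mg (A) and 160/160/160 mg (B); pre-dose troughs on days 7, 14 and 21; parent half-life 20 to 30 h and M5 half-life 60 h (section 1.31).

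**Assumptions.** Exposure proportional to dose^b, with b from 0.5 to 1.0; lognormal within-patient error with the same CV in both arms, 0 to 100%; one-compartment superposition.

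**Step 1: no random variability.** The pre-dose trough on day d is the sum, over earlier days i, of D_i^b × r^(d−i), where r = 2^(−24/half-life). At 28 h, r = 0.552, r^6 = 0.0283 and r^7 = 0.0156.

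- Arm B, day 21 over day 7: (1 − r^20)/(1 − r^6) ≈ 1/0.9717 = 1.03.
- Arm A, b = 1: 2 + 1.5 × r^6 × (1 − r^7)/(1 − r^6) + r^13 × (1 − r^7)/(1 − r^6) ≈ 2 + 0.043 + 0.0004 = 2.04.
- Arm A, b = 0.5: replace 2 by √2 = 1.414 and 1.5 by √1.5 = 1.225, giving 1.414 + 0.035 + 0.0004 = 1.45.

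Over half-lives of 20 to 30 h, Arm A is 2.01 to 2.06 (b = 1) or 1.42 to 1.46 (b = 0.5); Arm B is 1.01 to 1.04. For M5 at 60 h, Arm A is 1.69 (b = 0.5) to 2.33 (b = 1) and Arm B 1.23, because M5 is still accumulating.

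**Step 2: add random variability.** Median of the three-sample ratio at steady state, 400,000 simulated patients:

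| Assumed within-patient CV | Arm B | Arm A, b = 0.5 | Arm A, b = 1 |
|---|---|---|---|
| 10% | 1.17 | 1.43 | 2.00 |
| 20% | 1.37 | 1.55 | 2.05 |
| 30% | 1.59 | 1.73 | 2.18 |
| 50% | 2.12 | 2.23 | 2.60 |
| 60% | 2.41 | 2.52 | 2.88 |
| 100% | 3.74 | 3.86 | 4.22 |

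At planned doses Arm A is always higher. Escalation dominates at low CV and is a small part at high CV.

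**Step 3: departures from plan.** Nominal dose ratios (b = 1), using the dose levels in sections 8.1 and 8.2:

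- Arm A stepped down to 80/120/80: 120/80 = 1.5, against 160/80 = 2.0 with full escalation.
- Arm B reduced one level: 160/120 = 1.33; two levels: 160/80 = 2.0; against 1.0 with no reduction.

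**Step 4: number of samples.** A max:min ratio can only stay equal or rise when a sample is added. At constant dose, two against three samples gives 1.32 against 1.59 (CV 30%) and 1.57 against 2.12 (CV 50%). In Arm A with b = 1 and CV 30%, two samples (days 7 and 14) give 1.53 and three give 2.18.

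**Step 5: would dividing by dose repair it?** Only if b = 1. At b = 0.5 the dose-normalised troughs differ by 2/√2 = 1.41 with no variability at all, a false signal in the other direction.

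**The case against.** The strongest reply is that this is one descriptive example in an exploratory paragraph. The association with toxicity and efficacy that section 16.47 specifies is for the average concentration, not for this ratio. The plan does not commit to comparing the ratio between arms or to relating it to outcomes. That stands, and it limits the severity. It does not rescue the metric, because the plan labels it within-patient variability.

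Several stronger readings are tempting, and the documents do not support them:

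- **That the ratio measures escalation and not variability.** It mixes both. At an assumed CV of 50% and b = 0.5 the medians are 2.23 and 2.12, so almost all of Arm A's ratio is random variation. Which source dominates depends on a CV that the documents do not give.
- **That Arm A carries a two-fold exposure step.** Two-fold is the dose ratio. All three doses exceed 60 mg, where section 1.31 reports less-than-proportional PK, so for the parent drug it is an upper case.
- **That Arm A is bound to look more variable.** The table holds Arm B at 160 mg through day 21. Reductions and interruptions allowed in section 8 would raise Arm B's ratio, and the realised gap has not been modelled.
- **That early stoppers will look less variable.** This follows only if patients with fewer troughs are kept. If section 16.8 removes anyone with a missing trough, the sample count is fixed and the problem becomes selection of completers. The plan does not say which applies.

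It is also fair to say that a larger distortion sits in the same sentence. The off-drug Cycle 2 Day 1 sample puts the noise-free cycle 2 and overall parent ratios at about 49 (half-life 30 h) to 338 (20 h) in both arms. That is a separate defect; it does not affect the cycle 1 ratio, and one rewording can deal with both.

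**Conclusion.** The point holds as confounding. At planned doses, the cycle 1 ratio in Arm A contains a dose-escalation component that Arm B lacks. Before any random variation, that component makes the parent ratio about 1.4 to 2.0 in Arm A against about 1.0 in Arm B. At an assumed CV of 30% the median gap is 0.14 (1.73 − 1.59) to 0.59 (2.18 − 1.59). The direction at planned doses is certain. The size rests on the assumed exponent and CV, an equal CV in both arms, and a one-compartment model that ignores enterohepatic recirculation. Dose changes for toxicity and the unresolved handling of missing troughs add further non-PK content in both arms.

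Severity is minor: the analysis is exploratory and descriptive, and the primary endpoint is untouched.

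**What to change.** In section 16.47, replace the raw ratio with the within-patient SD of log trough, reported as a CV:

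1. Use on-drug troughs only. At the planned visits these are Cycle 1 Days 7, 14 and 21 and Cycle 2 Day 21; leave out Cycle 2 Day 1.
2. Take residuals of log trough around arm-by-time-point means, with actual recent dose as a covariate where it departs from plan.
3. For each patient compute the SD, s, of the residuals and report CV = √(exp(s²) − 1), per patient and summarised by arm, with the number of troughs used.
4. State how section 16.8 applies to a patient with a missing trough.

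Step 2 removes the planned escalation without knowing b: the term b × log(dose) is the same for every Arm A patient on plan at a given visit, so it is absorbed in the mean. It also absorbs M5 accumulation. A per-patient value is needed because a single residual variance per arm could not be related to individual toxicity or response.

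If a ratio is kept, restrict it to on-drug troughs at the same actual dose and compare arms on the same sample set. At planned doses, Arm A then has only Cycle 1 Day 21 and Cycle 2 Day 21, so it has no within-cycle ratio.

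The cost is SAP wording and one model on data already collected. A model-based summary replaces a simple ratio. With at most four on-drug troughs, each patient's SD is imprecise. In Arm A the dose effect is estimated only from departures from plan, many of them driven by toxicity, so results for off-plan patients need cautious reading.
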